6.4.2 Laboratory Parameters

Generally, only central laboratory measurements will be used for analyses. The only exception is for hematology, where a few countries have the possibility to use local labs in exceptional circumstances (e.g. logistical challenges due to global pandemic, natural disaster, or regional crisis). These local measurements will also be used for the analysis.

The number of participants with treatment-emergent (after the first dose of study drug and up to 3 days after last dose of study drug) abnormal laboratory values above or below the normal range will be tabulated by the laboratory parameter and treatment group.

Summary statistics including changes to baseline will be calculated by treatment group and visit for all quantitative laboratory parameters, e.g. for hematology, NT-proBNP, high sensitive troponin T (hs-TNT), clinical chemistry and urinalysis. Geometric statistics and ratios to baseline will be presented for urinary creatinine, albumin and UACR and NT-proBNP instead of arithmetic statistics with changes from baseline. For eGFR the relative change will be displayed in addition to the absolute change from baseline. Graphical displays will be provided for change from baseline and ratio to baseline by visit, respectively.

Proportion of patients with available and missing measurements will also be displayed.

Summary statistics for serum potassium, eGFR, NT-proBNP and serum creatinine will also be repeated by treatment group and visit separately for each level of the stratification factors.

The following special safety parameters will be further assessed by displaying the number of participants with safety events as described below by treatment group, visit and for any time treatment-emergent (including unscheduled assessments) and up to 3 days after last study drug administration. This will also be performed by stratification factors. The summaries will be performed for the number of participants with:

- Absolute value of serum potassium >5.0 mmol/L, >5.5 mmol/L (hyperkalemia), >6.0 mmol/L (severe hyperkalemia) and >7.0 mmol/L
- Relative decrease from baseline in eGFR of $\geq 25\%$, $\geq 30\%$, $\geq 40\%$, $\geq 50\%$ and $\geq 57\%$, also sustained decrease over 4 weeks
- Absolute value of eGFR < 30 ml/min/1.73m²
- Increase from baseline in serum creatinine >0.3 mg/dL and >0.5 mg/dL.

The percentage of participants with the respective events (non-stratified) at any time post-baseline (including unscheduled assessments) and within 3 days after last study drug administration will be compared between the finerenone and placebo group by applying separate explorative χ^2 tests with continuity correction. If the expected number of participants in at least 1 cell of the 2x2 contingency table is <5 (Agresti 2005), Fisher's exact test will be applied instead of the χ^2 test. Estimates and two-sided 95% CIs will be provided for each treatment group and the treatment differences. Clopper-Pearson CIs will be calculated for each treatment group, while for treatment differences the exact unconditional confidence limits will be calculated.

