### Treatment Period

Following a screening period of up to 2 weeks, eligible participants will be randomized in a 1:1 ratio to either finerenone or placebo. Participants with an eGFR  $\leq 60$  mL/min/1.73 m^2 measured at baseline will start with 10 mg OD (**dose level 1**) with a maximum maintenance dose of 20 mg OD (**dose level 2**), whereas participants with an eGFR  $> 60$  mL/min/1.73 m^2 measured at baseline will start with 20 mg OD (dose level 2) with a maximum maintenance dose of 40 mg OD (**dose level 3**).

There will be at least 2 scheduled visits within the first 3 months from randomization, Visit 2 will take place after 1 month and Visit 3 will take place 3 months after randomization; thereafter, scheduled visits will occur every 3 months until Visit 6 at Month 12. After 1 year from randomization, telephone contact visits will take place at Month 14 and from then onwards every 4 months (i.e. 18 months, 22 months onwards) *alternating* with on-site visits (i.e. 16 months, 20 months, onwards) until the end of the study is reached.

Up-titration is expected to occur after 4 weeks  $\pm$  7 days of treatment at Visit 2 (Month 1). Ideally, each participant will be on the maximum maintenance dose at this point. In the case of elevated potassium values, participants will be down-titrated to the next lower dose. Down-titrations can be performed at any time after the start of study intervention treatment, at any scheduled or unscheduled visit. At any scheduled or unscheduled visit, the dose of study intervention may be increased to the next possible higher dose, based on serum/plasma potassium level and provided the participant was already on a stable dose for 4 weeks  $\pm$  7 days.

Participants will attend an additional unscheduled safety visit 4 weeks  $\pm$  7 days after each up-titration; potassium levels and renal function will be monitored at this safety visit. In addition to the protocol-specified visits, participants may be seen at any time throughout the study at the discretion of the investigator.

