### 7.1.1      **Temporary Discontinuation**

#### **Resumption of study intervention after temporary interruption**

Upon temporary interruption of the study intervention due to hyperkalemia, eGFR decrease, (S)AE, outcome events (OE), intolerance or any other reason, intake should be resumed as soon as medically acceptable at the discretion of the investigator. There is no defined maximum time limit for temporary interruption. In all cases, the reason for study intervention interruption must be recorded in the eCRF and the participant's medical records.

If the study intervention is interrupted for more than 7 days, the re-start should be performed at the next lower dose and the investigator should schedule an up-titration visit after 4 weeks ( $\pm$  7 days) in order to monitor potassium levels and renal function (see [Table 6–1](#)). If a regular visit will be scheduled to take place 4 weeks  $\pm$  7 days after up-titration or re-start, the monitoring of potassium and renal function is assured and no up-titration visit has to be performed in addition. A restart and/or safety check visit is expected only if the investigator is aware of a temporary interruption that was initiated by the study participant.

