### Central Laboratory Assessment

The name and the address for the central laboratory service provider can be found in the documentation supplied by the vendor. Only centrally analyzed blood samples will be considered for statistical analysis, unless otherwise specified. Details of the collections, shipment of samples and reporting of results by the central laboratory will be provided to the investigators in the Laboratory Manual.

- Laboratory evaluations (hematology, HbA1c, clinical chemistry, urinalysis parameters, biomarkers [NT-proBNP and hs-TnT]) are shown in Section [10.2](#).
- SoA (Section [1.3](#)) for the timing and frequency.

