### Local Laboratory Assessment

Blood safety samples will be taken from the Screening Visit onwards for analysis at the local laboratory.

- The following clinical chemistry parameters must be measured and the values documented in the eCRF
  - Serum/plasma creatinine (eGFR will be calculated automatically in the eCRF using the CKD-EPI formula)
  - Serum/plasma potassium.

From visit 2 (Month 1) onwards, study participants may have their local laboratory assessments taken up to 3 days prior to the study visit.

Potassium values should be recorded using a single decimal point (e.g. 4.5 mmol/L or mEq/L). In the event of hyperkalemia, please see [Table 6–2](#) for guidance.

Up-titration or down-titration of the study intervention will be based on local potassium results and must be documented in the eCRF. Down-titration of the study intervention should occur primarily for safety reasons but can also be done for exceptional logistical reasons (e.g. study intervention supply issue).

Additionally, at screening, BNP or NT-proBNP can be measured if not available from clinical medical records.

In women of childbearing potential, a pregnancy test will be performed locally, at screening and baseline. Further pregnancy tests should be performed in participants of childbearing potential as required by national/institutional regulations (e.g. at every visit). At any time during study participation, additional pregnancy testing should be performed upon suspicion of pregnancy. Both serological and urine tests are acceptable.

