4.5.5 Other Data Handling

Only the data provided by the central laboratory will be used for analysis; values from local laboratories will not be used in the statistical analysis unless otherwise specified and will be listed only. For example, as described above, local values will be used in the derivation of baseline, if no central measurement is available (cf. Section 4.5.1).

At all visits post-randomization and if not stated otherwise, only the values at scheduled measurements will be used for analysis.

For the derived visit “Any time post baseline” (applicable for efficacy) this will include any measurement after randomization, including unscheduled assessments. For the derived visit

“Any time on treatment” (applicable for efficacy), only assessments on or after study medication start date until 30 days after last study drug administration, including unscheduled assessments, will be considered. For safety, “Any time treatment-emergent” will include measurements on or after study medication start date until 3 days after last study drug administration, including unscheduled assessments.

For values which are < LLOQ (Lower limit of quantification), half the value of the LLOQ will be used for analysis. Differences between two values < LLOQ will be assigned values of 0. Ratios between two values < LLOQ will be assigned a value of 1. For values which are > ULOQ (Upper limit of quantification), the ULOQ will be used for analysis.

In case of non-normally distributed data, descriptive statistics other than minimum, maximum and median will only be calculated if at least 2/3 of the individual data were measured and were above the lower limit of quantification. In tables showing descriptive statistics, where values below LLOQ are included, these descriptive statistics will be marked.

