Only central laboratory measurements before initiation of dialysis or renal transplantation will be considered for the definition of the individual eGFR-based components of the renal endpoint. At the up-titration, restart and safety check visits, only a local laboratory measurement is obtained. These values will be checked for a potential eGFR event and, in case of decline, the investigators will be advised to retest eGFR centrally in an unscheduled visit; determination of an eGFR event will then be based on this value. If an initial decrease in eGFR occurs on the EoS visit, there will be another confirmatory measurement taken at least 4 weeks later to confirm the initial decrease. The individual components “Sustained decrease of eGFR $\geq 50\%$ from baseline over at least 4 weeks” as well as “Sustained eGFR decline $<15\text{ml/min}/1.73\text{m}^2$ ” will be programmatically derived. Only in the event that the eGFR decrease was confirmed by at least one additional eGFR measurement taken at least 4 weeks later, it will be considered as a sustained decrease and counted for the renal endpoint. The confirmatory additional eGFR measurements will typically be taken during an unscheduled visit. The date used for the analysis will be the date of the initial sample exceeding the threshold. If there was no confirmatory assessment, events will only be counted for the renal endpoint when the patient died after the initial decrease or the patient went on renal replacement therapy such as dialysis or transplantation prior to their scheduled confirmatory assessment. If there is an intermediate measurement that does not confirm the initial decrease, the event will not be counted for the renal endpoint.

eGFR events will be counted from the day of randomization until the EoS visit (or EoS notification + 28 days if EoS visit is missing). Participants will be censored at the earliest of the date of their last visit when a central eGFR measurement is available or EoS visit date (or EoS notification + 28 days if EoS visit is missing). If no post-baseline eGFR measurement is available, participants will be censored at day 1 (randomization date).

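### The potassium threshold counts in SAP 6.4.2 leave out the local samples taken after each dose increase or restart, so they can understate laboratory hyperkalemia

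*SAP*

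**What the plan says.** **Which values are analysed.** For laboratory safety parameters, SAP 6.4.2 states: "Generally, only central laboratory measurements will be used for analyses. The only exception is for hematology". SAP 4.5.5 gives the general rule: "values from local laboratories will not be used in the statistical analysis unless otherwise specified and will be listed only". Protocol 8.2.3 agrees but leaves room for exceptions: "Only centrally analyzed blood samples will be considered for statistical analysis, unless otherwise specified". Under these rules SAP 6.4.2 tabulates potassium thresholds, relative falls in eGFR, eGFR below 30 and rises in creatinine, by visit and at any treatment-emergent time with unscheduled assessments included. It then compares the arms with chi-square or Fisher tests and confidence intervals.

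**Which values are collected after a dose change.** Protocol 4.1 (Treatment Period) requires an extra visit 4 weeks ± 7 days after each up-titration, at which "potassium levels and renal function will be monitored at this safety visit". On the laboratory used, SAP 6.2.2.1 says: "At the up-titration, restart and safety check visits, only a local laboratory measurement is obtained". Protocol 9.4.1.2 says the same, and the central-laboratory row of the main Schedule of Activities is empty in that column. Protocol 8.2.3 (Local Laboratory Assessment) adds: "Up-titration or down-titration of the study intervention will be based on local potassium results and must be documented in the eCRF".

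**The concern.** Hyperkalemia is named in Protocol 2.3 as an important identified risk, and the laboratory count is the measure of it that does not depend on an investigator's decision to report. A reader of SAP 6.4.2 who sees that unscheduled assessments are included would expect the post-titration checks to be among them. They are the main planned unscheduled potassium samples, yet they drop out because they are local. A participant whose local potassium is high at such a check, whose dose is then changed, and whose next central value is back below the threshold does not enter the laboratory count or its between-group test. The observed proportion above each threshold, in either arm, can therefore be too low.

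**Working it through.** The plan states no figure for this point, so there is none to reproduce. The check has four parts.

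**1. Can a scheduled visit stand in for the local check?** Protocol 7.1.1 drops the extra visit if a regular visit falls in the same window, because then "the monitoring of potassium and renal function is assured and no up-titration visit has to be performed in addition". Regular on-site visits do have central sampling. The first up-titration is expected "at Visit 2 (Month 1). Ideally, each participant will be on the maximum maintenance dose at this point". Inputs from the Schedule of Activities: one month is 30 days, Visit 2 is Month 1 ± 3 days, Visit 3 is Month 3 ± 3 days, and the check is 28 ± 7 days after up-titration.

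- Visit 2: 30 ± 3 = days 27 to 33.
- Check: earliest 27 + 21 = day 48, latest 33 + 35 = day 68, nominal 30 + 28 = day 58.
- Visit 3: 90 ± 3 = days 87 to 93.
- The windows do not overlap (68 < 87), so Visit 3 cannot replace the check.
- From dose increase to next central sample: shortest 87 − 33 = 54 days, longest 93 − 27 = 66 days, nominal 60.

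The same holds for an up-titration at Visit 3: the check falls on days 87 + 21 = 108 to 93 + 35 = 128, and Visit 4 (Month 6 ± 6 days) on days 174 to 186.

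**2. Is there a central backstop?**

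| Parameter | After an abnormal local value | Effect on the counts |
|---|---|---|
| Potassium | Protocol Table 6-2: dose action and a recheck within 72 hours; no central sample named | Not counted unless a later central sample is also high |
| eGFR, creatinine | SAP 6.2.2.1 and Protocol 9.4.1.2: advice to retest eGFR centrally; Protocol Table 6-3: central retest after 4 weeks for falls of 40% or more | Partly recovered; a fall that resolves before the retest is lost |

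**3. What would a loss do?** The documents give neither the event rates nor the share of cases seen only locally. All rates and shares below are assumptions. Formula: counted proportion = true proportion × (1 − share seen only locally). The assumed true proportions above 5.5 mmol/L are 12% on finerenone and 6% on placebo.

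| Local-only share, finerenone / placebo | Counted, finerenone / placebo | Difference (points) | Ratio |
|---|---|---|---|
| 0% / 0% | 12.0% / 6.0% | 6.0 | 2.00 |
| 10% / 10% | 10.8% / 5.4% | 5.4 | 2.00 |
| 40% / 40% | 7.2% / 3.6% | 3.6 | 2.00 |
| 25% / 10% | 9.0% / 5.4% | 3.6 | 1.67 |
| 40% / 10% | 7.2% / 5.4% | 1.8 | 1.33 |
| 10% / 25% | 10.8% / 4.5% | 6.3 | 2.40 |

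With about 3000 per arm (6000 / 2, SAP section 3), shares of 10% and 40% on finerenone are 3000 × 0.12 × 0.10 = 36 and 3000 × 0.12 × 0.40 = 144 participants. Equal shares lower both proportions and the difference but leave the ratio alone. Unequal shares move the ratio in either direction.

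**4. Is the direction of any imbalance known?** One argument says more is lost on finerenone: acting on a local value reduces active exposure before the next central sample, while a sham change on placebo does nothing. The opposite argument is that a persistent drug effect is likely to be seen again at a later central visit, whereas a chance excursion on placebo is not. Protocol 4.3 predicts potassium increases of 0.1, 0.2 and 0.2 mmol/L at 10, 20 and 40 mg. The step on up-titration is then 0.2 − 0.1 = 0.1 for those starting at 10 mg and 0.2 − 0.2 = 0.0, to one decimal, for those starting at 20 mg. These figures do not settle the direction.

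**The case against.** The central-only rule is pre-specified, applied consistently in both documents, and has a rationale: one laboratory and one assay. Local potassium may be serum or plasma, whereas the planned variable is serum potassium. Some local samples are also triggered by earlier results (72-hour rechecks, restart visits), so a pooled count gives more chances of detection to whichever arm has more high values. These points stand. They argue against replacing the central-only count, but not against showing a second count beside it.

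A reader might infer that a participant with a locally detected rise is never counted, or that the safety objective is answered without these measurements. The documents do not support that. SAP 6.1.5 summarises down-titrations and interruptions with their reasons by arm. SAP 6.4.1 treats hyperkalemia as an event of special interest, with treatment-emergent counts, hospitalizations, discontinuations, cumulative incidence and an interruption-based sensitivity analysis, none tied to central values. Central potassium is also taken at every scheduled on-site visit, so over long follow-up some of the same participants will be caught later. What remains is that recording as an adverse event depends on the investigator judging the change clinically relevant (Protocol 8.2.3), and a dose-change table is not a threshold count.

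**Conclusion.** The point holds in limited form. The laboratory-defined potassium counts omit the planned post-titration and restart samples and can understate laboratory hyperkalemia. The timing gap of 54 to 66 days after the expected first up-titration follows from the protocol's own windows and assumes up-titration at Visit 2. The eGFR and creatinine counts share the problem to a lesser degree.

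Three stronger readings go beyond the documents. First, that the omission favours finerenone by shrinking the between-arm difference: this is plausible, but it depends on assumed potassium dynamics, and the opposite imbalance is also possible. Second, that a particular fraction of cases is lost: no document gives the local-only share, and any figure would change with the length of follow-up and with the threshold (SAP 6.4.2 counts values above 5.5, Protocol 9.4.2 values of 5.5 or more). Third, that these are the highest-risk measurements: the visits exist for monitoring, but no data in the documents rank their risk. The point is a cheap improvement, not an error in the plan.

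**What to change.** Keep the central-only threshold counts and the by-visit summaries as they are. Add to SAP 6.4.2, with a matching exception in SAP 4.5.5, a pre-specified parallel count at any treatment-emergent time and the same between-group comparison, using central plus local eCRF values. Potassium comes first, with creatinine and eGFR as secondary. Use the same thresholds and treatment-emergent window in both versions and print them side by side. State that the post-titration and restart checks are local, so that the reader knows which samples the central-only version excludes.

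The cost is SAP wording and one extra derivation. Protocol 8.2.3 already requires local potassium and creatinine in the eCRF, where eGFR is calculated, and SAP 4.5.1 already allows local values as a baseline fallback. The downsides should be stated with the table: local assays vary more and use serum or plasma, some local samples are prompted by earlier results, and the counts will rise somewhat.
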